CHOICE Study Protocol with Statistical Analysis Plan

NCT Number: NCT03576924

Document Date: March 3, 2025

Participants

Potentially eligible participants for this trial were referred by their family physician to partake in a community-based DPP (Small Steps for Big Changes) if they had a hemoglobin A1c (HbA1c) test within the American Diabetes Association's (ADA) prediabetes range of 5.7%-6.4% in the last 6 months. Potential participants who did not have a recent HbA1c test result but scored a 5 or higher on the ADA diabetes risk assessment were also invited to participate. Advertisements for recruitment included pamphlets in healthcare offices, website adverts, social media posts, and word of mouth. Potential participants were screened by a member of the research team via phone to ascertain if they met the following inclusion criteria: between 18 and 75 years of age, engaged in two or fewer bouts of purposeful physical activity per week in the last 6 months, had a recent HbA1c test result between 5.7%-6.4% or an ADA risk assessment score >5, and were cleared to engage in physical activity as determined by the Get Active Questionnaire. Participants were excluded from this trial if they had a previous diagnosis of T2D, were taking glucose-lowering medications or beta-blockers, had a history of cardiovascular disease, were diagnosed with uncontrolled hypertension (resting blood pressure >160/90), or had explicit contraindications to exercise. All participants provided written informed consent prior to enrollment.

Predicted Maximal Exercise Testing

Participants who met the eligibility criteria and provided consent subsequently completed a 12-lead electrocardiogram stress test at a local cardiac rehabilitation clinic supervised by a certified exercise physiologist prior to beginning the intervention. Depending on each participant's baseline physical ability and/or comfort level with treadmills, the exercise physiologist employed a Bruce or Modified Bruce protocol for the stress test. Protocol stages were performed on a treadmill and incremented sequentially every 3 minutes until participants reached volitional exhaustion or the test was stopped by the exercise physiologist according to safety cut-offs (blood pressure >250/120, oxygen saturation <82%, physical concerns). Participants' heart rate, blood pressure, oxygen saturation, and perceived rating of exertion (RPE) were monitored at each stage of the protocol. Stress test results were reviewed by a cardiologist to determine whether exercise was safe for the individual or whether any underlying cardiac issues were present that needed further attention. Additionally, results from the stress test were used to measure each participant's resting heart rate and maximum heart rate (HR_{max}) to calculate individualized exercise intensity zones for the intervention. This test also served to estimate cardiorespiratory fitness based on the total test duration (details found in supplemental material). The 12-lead electrocardiogram test was repeated with each participant 6 months postintervention to assess changes in cardiorespiratory fitness.

Small Steps for Big Changes

Participants that were cleared to exercise by a cardiologist were enrolled in *Small Steps for Big Changes* (SSBC), a 4-week community-based DPP. The full details of SSBC, including its efficacy and effectiveness in laboratory and community settings have been published previously. Briefly, SSBC consists of six one-on-one sessions with a trained community coach (i.e., fitness professionals working at a recreation facility) over a 4-week period, delivered either virtually or in-person at one of three community recreation facilities. Each session entails a brief behavioral counselling component during which trained coaches use motivational interviewinginformed techniques to foster participants' self-efficacy and determination for changing and maintaining healthy nutritional and physical activity behaviors. Information pertaining to specific content delivered during sessions and fidelity of program delivery by community coaches has been previously published. Community coaches subsequently follow up with participants 1, 6, and 12 months after the 4-week supervised intervention.

In addition to behavioral counselling, SSBC participants also complete supervised progressive exercise during each of the six sessions. For this trial, SSBC participants provided additional consent for a sub-study for which they were randomly allocated to one of three conditions: HIIT was introduced and performed for all 6 sessions (HIIT-only); MICT was introduced and performed for all 6 sessions (MICT-only); and HIIT and MICT were introduced during sessions 1 and 2 in a randomized counterbalanced order, and participants were provided the choice of which exercise to perform during sessions 3-6 (CHOICE). In all three conditions, participants were able to choose whether to exercise on a treadmill, exercise bicycle, or elliptical. Exercise duration for each session was designed to elicit matching work volumes based on prescribed intensities for both HIIT and MICT during the progressive nature of the intervention. The use of progressive exercise was intended to help familiarize participants with exercise modalities they may not have been familiar with and/or ease the introduction of exercise to those who were previously insufficiently active. Exercise was individualized for each participant by prescribing exercise intensities based on their measured resting heart rate and HR_{max} from the stress test using the Karvonen formula. Exercise intensity compliance was measured during each exercise session via heart rate monitors and participants' RPE. Exercise intensity was recorded by the supervising community coach at the beginning and at 25%, 50%, and 100% of exercise completion, and coaches encouraged participants to adjust speed, resistance, or incline if target heart rate was not achieved. Following the 4-week supervised intervention, participants in all three conditions were encouraged to continue performing MVPA on their own according to Canada's physical activity recommendations for adults but were not told to exclusively perform

either HIIT or MICT due to the pragmatic nature of the SSBC program and this trial. Apart from condition allocation, all other aspects of the DPP were identical for all three conditions.

High-Intensity Interval Training. Participants who were randomized to the HIIT-only condition began each exercise session with a 3-minute warmup at a comfortable self-selected pace. During sessions 1 and 2, participants completed five 30-second intervals >80% HR_{max} interspersed by four 60-second periods of light recovery at a self-selected pace. For sessions 3 and 4, duration of high-intensity intervals increased from 30 seconds to 45 seconds, and for sessions 5 and 6, duration was increased again to 60 seconds, so that by the end of the supervised intervention, participants were completing five 60-second intervals interspersed by four 60-second recovery periods. All sessions concluded with a 2-minute cooldown. Including warmup and cooldown, the total duration of sessions ranged between 11.5 to 14 minutes for sessions 1 to 6, respectively.

Moderate-Intensity Continuous Training. Participants who were randomized to the MICT-only condition exercised continuously for 20 minutes at an intensity between 60%-80% HR_{max} during sessions 1 and 2. Duration of exercise was increased to 25 minutes for sessions 3 and 4, and to 30 minutes for sessions 5 and 6. There were no warmup or cooldown periods, resulting in total session durations ranging from 20 to 30 minutes for sessions 1 to 6, respectively.

Choice. Participants who were randomized to the CHOICE condition were introduced to either HIIT or MICT during session 1 and introduced to the other exercise modality during session 2. The introduction order of HIIT or MICT was randomized in a counterbalanced fashion to diminish potential anchoring bias. HIIT and MICT protocols were the same as in the other two conditions, and progression of exercise followed the same convention.

Outcomes

For full details regarding outcome measures of this trial, please refer to the trial registry details. Briefly, individuals' perceived autonomy support was measured post-intervention to discern any differences between conditions. Within-condition changes in motivation regulation from pre-intervention were assessed post-intervention and 6-months post-intervention. Within-condition changes in free-living physical activity and cardiorespiratory fitness were assessed from pre-intervention to 6-months post-intervention. Between-condition differences were also assessed at each timepoint for motivation regulation, physical activity, and cardiorespiratory fitness. A manipulation check was conducted with a sub-set of participants to determine the modality of exercise that participants engaged in during the 6-month follow-up period.

Changes Consequent to COVID-19

Recruitment for this trial commenced in February 2019 using a monthly rolling recruitment strategy (~6-10 participants/month). Originally, follow-up appointments were planned to discern changes in the outcome variables 12 months post-intervention. However, at the beginning of the 12-month follow-up phase (February 2020), the COVID-19 pandemic resulted in the curtailment of all research activities at the host institution. A total of 75 participants were not able to complete follow-up assessments, and data were therefore lost for this first cohort. Recruitment for this trial could not be resumed until October 2021. To complete data collection in a timely manner given these unanticipated resource constraints, follow-up assessments were conducted 6 months post-intervention for this second cohort as opposed to the original 12-month timepoint. The complete loss of data on the first 75 participants to enroll in the trial and subsequent curtailment of research for more than 1.5 years therefore significantly limited the final study sample size.

Sample Size

Limited studies have been conducted that assess perceived autonomy support after adults are provided a choice between different types of exercise in an intervention. A study by Lonsdale and colleagues assessed the change in perceived autonomy support among adolescents enrolled in physical education programs. Comparisons between the control group (treatment as usual) and a group that was provided choice in what exercises were performed during class demonstrated a small-to-medium effect favoring the choice group (d = 0.39). Based on these results, we anticipated a crude small-to-medium effect size in favor of the choice condition in the present study ($d = \sim 0.40$). At an alpha level of .05 and 80% power, we estimated that 60 participants per condition (n = 180) were required to detect significant between-condition differences at this magnitude. Based on pilot findings by Locke and colleagues, this sample size was then increased by 20% to account for participant attrition, resulting in a total sample size of 216. The severe COVID-19 pandemic limitations impacted the ability to achieve the estimated sample size and data are thus reported for N = 77.

Randomization

SSBC participants were randomly allocated into one of the three arms of this study in a 1:1:1 allocation ratio by using a computer random-number generator that produced variable permuted block sizes. Conditions were stratified for biological sex (male and female) and age (18-45 and 46-75 years). Allocation sequencing was performed by a member of the research team not involved in any other aspect of this trial and allocation was concealed from participants until they began the intervention.

Blinding

Given the pragmatic nature of this trial and the fact that participants and community coaches needed to know which exercise modality to engage in during the exercise sessions, blinding of participants and those delivering the intervention was not possible. Data collected for each participant were blinded during data analysis by replacing the name of the allocated condition with a numerical digit known only to a member of the research team not involved in the data analysis phase so that data analysts would not be biased by condition allocation.

Statistical Methods

Statistical analyses were performed using R (version 4.3.0) or SPSS (version 28). Anthropometric and demographic information were summarized as means (standard deviations) for continuous data and N (%) for categorical data, unless otherwise stated. Medians and ranges are reported for 6-month exercise modality frequency to represent the central tendency and dispersion more accurately.

Blinded data analysis was completed on an intention-to-treat (ITT) basis as all randomized participants were included in the analyses irrespective of their program compliance. No missing data were imputed as per contemporary guidelines. A linear model with restricted maximum likelihood estimation (REML) was used to detect a between-condition difference in perceived autonomy support post-intervention. The model included treatment condition (i.e., HIIT, MICT, or CHOICE) as a fixed factor, and stratified allocation factors (i.e., age and biological sex) as covariates. Similarly, linear mixed models were used to analyze changes in motivation regulation, physical activity behavior, and cardiorespiratory fitness between conditions. Linear mixed models included fixed effects for timepoint (pre-intervention, postintervention, 6 months post-intervention), treatment condition, as well as the interaction thereof, stratified allocation factors, and a random effect for participants to address non-independence of measurements arising due to the repeated-measures design of this study. Model assumptions were assessed visually using normal probability plots and residuals vs. fitted values plots (i.e., homoscedasticity). Bonferroni-adjusted preplanned pairwise comparisons of estimated marginal means were conducted to derive effect estimates and accompanying 95% confidence intervals (CIs) after adjusting for included covariates. A two-sided alpha of .05 was used for all statistical analyses.

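### Sixty per condition gives about 58% power for d = 0.40 under the two-sided pairwise test the plan describes (47% or 41% with Bonferroni over two or three pairs), not the stated 80%

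*Combined protocol and SAP*

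**What the plan says.** All places are in the combined protocol and SAP.

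- **Sample Size.** The assumed effect comes from a two-group comparison in adolescents, choice against treatment as usual, with d = 0.39. From this, "we anticipated a crude small-to-medium effect size in favor of the choice condition in the present study", taken as d of about 0.40. "At an alpha level of .05 and 80% power", the section continues, "we estimated that 60 participants per condition (n = 180) were required to detect significant between-condition differences at this magnitude". For attrition, "this sample size was then increased by 20% to account for participant attrition, resulting in a total sample size of 216". After the pandemic, "data are thus reported for N = 77".
- **Outcomes.** The outcome used for sizing is measured once: "perceived autonomy support was measured post-intervention to discern any differences between conditions".
- **Statistical Methods.** A linear model with condition as a three-level factor, plus age and sex, "was used to detect a between-condition difference in perceived autonomy support post-intervention". Effect estimates come from preplanned comparisons between pairs of conditions, Bonferroni-adjusted. Alpha is .05, two-sided, for every analysis. The number of pairs in the adjustment is not given.
- **Randomization.** Allocation is 1:1:1 to three arms.

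**The concern.** The figure of 60 per condition is the only quantitative justification of the sample size, and it looked too small for d = 0.40. The familiar two-sided, two-group calculation at 80% power asks for about 100 per group, before any adjustment for multiple pairs. Because perceived autonomy support is measured only after the intervention, no baseline value or repeated measurement is available to recover precision.

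At stake is how the trial's results are read. The section presents 180 (216 with attrition) as an adequate target that the pandemic prevented the trial from reaching. If the target was itself too small for the stated effect, a reader who starts from d = 0.40 at 60 per arm and scales down to 77 participants will expect too much of the data and may misread a null result.

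**Working it through.** **Inputs.** d = 0.40, alpha .05, power 80% and n = 60 per condition (Sample Size); two-sided testing and Bonferroni-adjusted pairs (Statistical Methods); equal arms (Randomization). The effect is standardised, so no SD is needed.

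**1. Can the plan's figure be reproduced?** For one pair, two-sided, normal approximation:

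n per arm = 2(1.960 + 0.842)² / 0.40² = 2 × 7.849 / 0.16 = 98.1, so 99 (100 with the exact noncentral t).

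The stated 60 is not reproduced. The attrition step is: 180 × 1.20 = 216.

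**2. Power at 60 per arm, one given pair.** The standardised signal is 0.40 × √(60/2) = 2.191. Normal-approximation power is Φ(2.191 − z):

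- unadjusted, z = 1.960: Φ(0.231) = 59.1%
- two pairs, alpha .025, z = 2.241: Φ(−0.050) = 48.0%
- three pairs, alpha .0167, z = 2.394: Φ(−0.203) = 42.0%

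Exact noncentral-t results:

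| Adjustment | Power at 60/arm | n/arm for 80% | Detectable d at 60/arm | Power at 72/arm (216, no loss) |
|---|---|---|---|---|
| None | 58.4% | 100 | 0.52 | 66% |
| Two pairs | 47.1% | 121 | 0.57 | 55% |
| Three pairs | 40.9% | 133 | 0.60 | 49% |

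Using the error degrees of freedom of the three-arm model instead of the two-sample value changes power by less than half a point. With d = 0.39, unadjusted power falls to 56.3%.

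**3. More favourable readings.** Each is at 60 per arm; those involving three arms take CHOICE as 0.40 SD above both others.

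- Omnibus F: f² = (2/9) × 0.40² = 0.0356, so f = 0.189; noncentrality 180 × 0.0356 = 6.4; power 61%, with N = 276 needed. Setting f = d/2 = 0.20 instead gives 66%, with N = 246 needed.
- One-sided, single pair: 70%; 78 per arm needed.
- CHOICE against the other two arms pooled: signal 0.40 / √(1/60 + 1/120) = 2.530. Two-sided exact power is 71% (75 per arm needed); one-sided it is 81% (59 per arm needed).
- At least one significant CHOICE pair (simulation, 400,000 replicates): 75% unadjusted, 64% with Bonferroni over two pairs, 57% over three.

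**4. Could adjusting for age and sex close the gap?** If d is on the unadjusted SD scale, the share of outcome variance they must explain for one unadjusted pair is 1 − (0.40/0.516)² = 0.40. For the two-sided pooled contrast, with detectable d = 0.445, it is 1 − (0.40/0.445)² = 0.19. The document gives no such figure.

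**5. At N = 77.** With 77/3 = 25.7 per arm and nothing missing, the d detectable with 80% power is about 0.80 unadjusted, 0.88 for two pairs and 0.93 for three.

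**The case against.** The best case for the plan is that the Sample Size section leaves the test open, so the figure is unexplained rather than shown to be miscalculated. The section states a directional effect taken from a choice-versus-no-choice comparison, and HIIT-only and MICT-only are both arms without a choice of exercise type. A one-sided contrast of CHOICE against those two pooled needs 59 per arm, very close to the stated 60, and may be how the figure arose. This stands in part: one cannot say that no calculation yields 60. It does not rescue the statement, because the document nowhere describes that contrast and applies two-sided testing to all analyses. If it was the basis, the sizing and the analysis still disagree.

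A second argument is that covariates might help more than a single-pair calculation suggests: 19% of outcome variance would be enough for the two-sided pooled contrast. The figure is correct, but it needs both an undescribed contrast and an unsupported assumption about age and sex.

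Third, the document is retrospective, the target was never reached, and no estimate depends on it. That limits the consequences to interpretation. It does not make the power statement correct.

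**Conclusion.** The concern holds. Under the two-sided pairwise analysis in Statistical Methods, the stated 80% is too high by about 22 percentage points for one given pair unadjusted (80 − 58.4), 33 with Bonferroni over two pairs (80 − 47.1) and 39 over three (80 − 40.9). The stated 60 is 60% of the unadjusted requirement (60/100) and 45% of the three-pair requirement (60/133). Enrolling all 216 with no loss would still not give 80% for a given pair.

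This rests on equal arms, a common SD, d expressed on the unadjusted SD scale, and the pairwise comparison being the test that matters. The omnibus F and the two-sided pooled contrast also fall short of 80%. How far Bonferroni lowers power depends on the unstated number of pairs. Which calculation actually produced 60 remains unknown.

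**What to change.** 1. In Sample Size, state the test, contrast, sidedness and number of Bonferroni-adjusted pairs behind the figure of 60.
2. If that is not the analysis in Statistical Methods, say so and restate the power. Suggested text:

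> With 60 participants per condition, a two-sided pairwise comparison at alpha .05 has 80% power for d of about 0.52 (0.57 with Bonferroni over two pairs, 0.60 over three). Detecting d = 0.40 would have needed about 100 (121 or 133) per condition.

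   Keep only the figures for the number of pairs actually adjusted for.
3. Optionally, add the detectable d at N = 77 from step 5 of the working, with its assumption of equal arms and no missing data.

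The cost is a recalculation, a few sentences and a less favourable stated power. No participants are added and the analysis does not change.

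### The mixed models for motivation, physical activity and fitness leave pre-intervention means free by condition, so between-condition estimates lose precision that the collected baseline could supply

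*Combined protocol and SAP*

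**What the plan says.** Statistical Methods states that "linear mixed models were used to analyze changes in motivation regulation, physical activity behavior, and cardiorespiratory fitness between conditions". The fixed effects are timepoint, with pre-intervention as one of its levels, and then "treatment condition, as well as the interaction thereof, stratified allocation factors, and a random effect for participants". The stratification factors are age and biological sex, in line with Randomization: "Conditions were stratified for biological sex (male and female) and age (18-45 and 46-75 years". No baseline value of the outcome is listed as a covariate, and no term makes the pre-intervention means equal across conditions.

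On effect estimates the section says "Bonferroni-adjusted preplanned pairwise comparisons of estimated marginal means were conducted to derive effect estimates". It does not say whether the means compared are those at a single timepoint or changes from pre-intervention.

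Outcomes says "Between-condition differences were also assessed at each timepoint for motivation regulation, physical activity, and cardiorespiratory fitness". For change it says "Within-condition changes in free-living physical activity and cardiorespiratory fitness were assessed from pre-intervention to 6-months post-intervention", with a similar statement for motivation at post-intervention and 6 months. It also sends the reader elsewhere: "For full details regarding outcome measures of this trial, please refer to the trial registry details".

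Sample Size gives a target of 216 and then reports that "data are thus reported for N = 77". Perceived autonomy support, on which the trial was sized, is measured post-intervention only and has its own linear model.

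**The concern.** A condition main effect with a full condition-by-timepoint interaction lets the pre-intervention means differ freely between the three conditions. Randomisation makes them equal in expectation, but the model does not use that fact. With complete data, a difference at follow-up then draws nothing from the pre-intervention value. A difference in change does use it, but only by plain subtraction, whatever the correlation. The participant random effect handles the dependence between repeated measurements. It does not supply baseline adjustment of the between-condition contrast.

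Two things are at stake. With 77 participants the intervals for these outcomes will be wide, and the plan leaves available precision unused. In addition, the two possible contrasts differ by the chance baseline difference between conditions, so a reader cannot be sure which one a reported between-condition result is.

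**Working it through.** **Plan's own figure.** The documents give no precision or sample size figure for these three outcomes, so there is none to reproduce.

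**Inputs.** N = 77 (Sample Size) and 1:1:1 allocation (Randomization) give n = 77/3 = 25.7 per condition, with equal split assumed because per-condition counts are not given. Also assumed: equal SD over time, and ρ, the pre/follow-up correlation after allowing for age and sex. The documents give no ρ, so 0.3, 0.5 and 0.7 are shown. Results are in residual SD units.

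**Formulas, complete data, one pairwise contrast.**
- Difference at a timepoint: SE = √(2/n)
- Difference in change: SE = √[(2/n) × 2(1 − ρ)]
- Baseline-adjusted or common-baseline: SE = √[(2/n) × (1 − ρ²)]

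Here 2/n = 0.0779, so the first SE is 0.279 at every ρ. At ρ = 0.5 the adjusted SE is √(0.0779 × 0.75) = 0.242.

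| | ρ = 0.3 | ρ = 0.5 | ρ = 0.7 |
|---|---|---|---|
| SE, difference at a timepoint | 0.279 | 0.279 | 0.279 |
| SE, difference in change | 0.330 | 0.279 | 0.216 |
| SE, baseline-adjusted | 0.266 | 0.242 | 0.199 |
| Cut against timepoint, 1 − √(1 − ρ²) | 5% | 13% | 29% |
| Cut against change, 1 − √[(1 + ρ)/2] | 19% | 13% | 8% |
| Equivalent N against timepoint, 77/(1 − ρ²) | 85 | 103 | 151 |
| Equivalent N against change, 77 × 2/(1 + ρ) | 118 | 103 | 91 |

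A generalised least squares calculation with the stated fixed-effect structure (age and sex absorbed into the residual SD) and a random-intercept covariance gave the same complete-data variances with two visits and with three.

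**Missing follow-up.** The amount is not given. With two visits and a fraction m missing at random at follow-up, the variance factors are (1 − ρ²)/(1 − m) for the adjusted contrast, the same plus ρ² for a timepoint difference, and the same plus (1 − ρ)² for a change difference. At m = 0.3 and ρ = 0.5 these are 0.75/0.7 = 1.071 and 1.071 + 0.25 = 1.321, a cut of 1 − √(1.071/1.321) = 10%. Over the three ρ values at m = 0.3 the cuts are 3% / 10% / 23% against timepoint and 15% / 10% / 6% against change.

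**Effect of a chance baseline difference.** The SE of the baseline difference is also 0.279, so a difference of 0.3 SD is unremarkable. It shifts the timepoint contrast by 0.3ρ = +0.09 / +0.15 / +0.21 and the change contrast by −0.3(1 − ρ) = −0.21 / −0.15 / −0.09. The two estimates then differ by 0.3 SD.

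**Validity check.** A simulation of the stratified design with 77 participants (8,000 runs per ρ, complete data, assumed stratum sizes) gave type I error of 4.3% to 5.4% for all three methods. It fitted separate linear models, not the mixed model itself, so it supports the general point about validity and not exact figures.

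**The case against.** The stated model is valid and widely used, and it delivers the within-condition changes that Outcomes asks for. No wrong conclusion follows from it, and the outcome on which the trial was sized is untouched. This all stands: the point is about efficiency.

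The size of the gain is not known. It rests on an assumed ρ and is small at one end of each reading (5% against timepoint at ρ = 0.3, 8% against change at ρ = 0.7). The equivalent N of 151 needs both the timepoint reading and ρ = 0.7; at the same ρ the change reading gives 91. The main reason for wide intervals is 77 participants against 216, which adjustment does not repair. This stands too, and is why ranges are shown.

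A reader might infer that Outcomes and Statistical Methods contradict each other. The documents do not support that. One condition-by-timepoint model yields both contrasts, and the documents also use the word change loosely in describing follow-up of fitness and of the outcomes generally. The registry, which is not available here, may define the contrast. What remains is an ambiguity. The missing adjustment would remain even with a contrast defined there, because the model terms are listed in Statistical Methods.

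Finally, one form of adjustment has its own cost. With baseline as a covariate and only post-baseline outcomes, anyone without a post-baseline value leaves the model. That sits badly with the statement that all randomised participants were analysed without imputation. This objection decides the choice of remedy below.

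**Conclusion.** The point holds as a loss of precision for between-condition estimates of three outcomes. The loss occurs under either reading of the contrast: for any ρ above 0 against a timepoint difference, and for any ρ below 1 against a change difference. At ρ = 0.5 with complete data, adjustment would be worth analysing about 103 participants instead of 77. The size depends on ρ, equal allocation, equal SD over time and the unknown extent of missing follow-up.

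A reader might infer that the results are biased or that false positives are inflated. Neither follows under randomisation. Within-condition changes and perceived autonomy support are outside the point.

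**What to change.** Fit the same mixed model with one pre-intervention mean common to all conditions. Keep timepoint, condition-by-post-baseline-timepoint terms, age, sex and the participant random effect, and drop the condition main effect. Report the between-condition difference at each post-baseline timepoint, and name that contrast in both Outcomes and Statistical Methods. With a common baseline, the difference at a timepoint and the difference in change are the same quantity, so the ambiguity goes as well.

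This needs no new data: one extra model per outcome and one sentence. It retains every randomised participant with any measurement. Its downside is that it gives no pre-intervention comparison between conditions, which under randomisation reflects only chance.

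Baseline as a covariate with post-baseline outcomes only is acceptable if the plan states that participants without a post-baseline value drop out. For physical activity and fitness that means everyone missing the 6-month visit. The extra parameter costs little: variance × (1 + 1/70), about 0.7% on the SE, where 70 = 77 − 5 − 2.

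If results are already known, report the new model beside the stated one as a labelled post hoc sensitivity analysis, not as a replacement.
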